#### 4.3.4.1 HISTOLOGY EVALUATION OF BIOPSY TISSUE

Tissue samples will be assessed via microscopy, histology, and immunohistochemistry for biological markers of elasticity (collagen density, elastin, fibrillin-1) and hydration (HA) at Baseline and Day 180.

[figure not shown]
The density of dermal collagen is an indicator of skin elasticity because of collagen's role in maintaining the strength of the skin, helping it to resist mechanical deformation. Other biological markers of elasticity are fibrillin-1, a glycoprotein that supports the integrity of the dermal elastic fiber network, and elastin, an essential protein of the elastic fibers of the skin, such as oxytalan and elaunin. Well-studied biological markers of skin hydration include aquaporin-3 (AQP3), water- and glycerol-transporting membrane proteins expressed in the epidermis and glycosaminoglycans (GAGs), which are linear polysaccharide molecules, including HA, that bind water and help regulate the hydration of the dermis.

Two living human skin tissue samples will be collected at baseline during the facelift procedure prior to any treatment with the Renuvion APR system and at Day 180 post-surgery (D180) during the follow up visit. Skin punch biopsies ranging from 3-5 mm in diameter will be obtained from left side of the face. One tissue sample will be taken from the untreated portion of the face within 2cm of the Root of the Helix and 2cm of the hairline. Measures should be taken to ensure the biopsy is taken from facial skin, rather than scalp skin. The second tissue sample will be obtained from cheek skin in the untreated area of the lower face within 2 cm of the treatment line. See **Figure 3**. Both biopsies will be taken prior to any treatment with the Renuvion APR System at Baseline and then again after treatment at the same locations at D180. The untreated skin tissue samples from non-surgical sites for each subject will be provided as control specimen. The tissue samples will be fixed in 10% neutral buffered formalin and prepared for histological and immunohistochemical assessments. In brief, tissues will be gross-trimmed, dehydrated, oriented

 Apyx Medical Corporation	
Protocol Number: APX-21-04	Effective Date: March 19, 2024 Revision No: 7.0
Title: Histological Evaluation of Human Skin Biopsies to Assess the Effects of Renuvion APR Treatment as an Adjunct Procedure in Facelift Surgery	

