## 7.2 STUDY PROCEDURE

The lower facelift surgery will be performed as per the investigator's standard clinical practice. The Renuvion APR System treatment will be performed using 4 treatment passes with settings of 80% and 1.5 LPM of helium flow with an activation speed of approximately 1-3cm/s. See **Section 4.3.4.1** for detailed instructions regarding collection, storage, and shipment of punch biopsy tissue samples. For all subjects the Renuvion APR System will be used in open surgery between the skin and SMAS on the neck, submentum, and lower facial skin flap. The mid/upper-face area will not be treated with Renuvion. A video or photograph of the face after the biopsies will be taken prior to Renuvion treatment to ensure proper location of punch biopsies at the D180 visit.

Procedure data and adverse events will be captured.

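### The Day 180 punches are sent back to the baseline punch sites with no rule to avoid the scar, so change from baseline may not be separable from healed wound or displaced skin

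*Combined protocol and SAP*

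**What the plan says.** All references are to the combined protocol.

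- **Punch size and side (Section 4.3.4.1).** "Skin punch biopsies ranging from 3-5 mm in diameter will be obtained from left side of the face".
- **Upper site.** A zone in the part of the face that the device does not reach, bounded by 2 cm limits from two landmarks: the helical root and the hairline.
- **Lower site.** "The second tissue sample will be obtained from cheek skin in the untreated area of the lower face within 2 cm of the treatment line".
- **Timing and place.** Each site is punched before device use at baseline, and "then again after treatment at the same locations at D180".
- **Control.** "The untreated skin tissue samples from non-surgical sites for each subject will be provided as control specimen". I take this to be the upper site.
- **Relocation (Section 7.2).** "A video or photograph of the face after the biopsies will be taken prior to Renuvion treatment to ensure proper location of punch biopsies". This refers to the second set of punches. The same section places the device treatment in open surgery under a lower facial skin flap and leaves facelift technique to the investigator.
- **Use of the tissue.** Outcome 1 (Section 4.3) compares the untreated with the treated portion of the face at D180 and also with baseline. Outcome 10 is change in estimated skin age from baseline to D180; Section 4.3.4.8 measures it on tissue left over from the same biopsies. Section 10.1 plans descriptive statistics only.

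No section gives a minimum distance from the baseline punch, tells the operator to avoid its scar, or says whether a location means the original skin or the facial landmark. The biopsy-location figure was not available in the text reviewed.

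**The concern.** A 3-5 mm punch removes the skin it samples, and what fills the hole is repair tissue. The readouts are collagen density, elastin, fibrillin-1 and a semi-quantitative score of dermal fibre integrity. That repair tissue differs from intact dermis on such measures is a general premise of mine, not a statement in the protocol. If it holds, a D180 sample cut through the old wound shows a change that has nothing to do with the device.

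The upper zone is defined by anatomical landmarks that staff can find unaided. What a photograph taken after the biopsies adds is the position of the first punches, and its stated purpose is "to ensure proper location of punch biopsies at the D180 visit". Sites that follow both sections faithfully could aim at the healed wound.

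The lower-face site has a second problem. Skin on or near a raised flap may not lie over the same facial point afterwards. The operator may therefore sample the same scar or different skin, and the plan does not say which is intended.

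Section 7.3.2 calls the D180 visit the primary endpoint. Enrolling more subjects would not remove this kind of bias, and contaminated tissue cannot be corrected in the analysis.

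**Working it through.** The plan states no figure to reproduce: the sample size is up to 10 treated subjects without a derivation. The checks below take the punch diameter (3-5 mm) and the 2 cm zone limits from Section 4.3.4.1. Offsets, placement errors, zone shapes and effect sizes are assumptions.

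**1. Share of the D180 punch that is old wound.** For two discs of equal diameter d with centres c apart, and x = c/d, the overlap as a fraction of one disc is (2/π)[arccos(x) − x√(1 − x²)]. For d = 4 and c = 1, x = 0.25, so (2/π)(1.318 − 0.242) = 0.685.

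| Offset c | d = 3 mm | d = 4 mm | d = 5 mm |
|---|---|---|---|
| 0 mm | 100% | 100% | 100% |
| 1 mm | 58% | 69% | 75% |
| 2 mm | 22% | 39% | 51% |
| 3 mm | 0% | 14% | 29% |

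This treats the healed wound as keeping its full diameter. Zero overlap needs centres at least d apart, that is 3 to 5 mm.

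**2. Chance of any overlap.** If the punch is aimed at the old site with placement error s on each axis, P(c < d) = 1 − exp(−d²/(2s²)). If it is instead re-sited at random, the chance comes from simulating pairs of points (2 million draws).

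| Scenario | d = 3 mm | d = 5 mm |
|---|---|---|
| Aimed, s = 1 mm | 99% | 100% |
| Aimed, s = 2 mm | 68% | 96% |
| Aimed, s = 3 mm | 39% | 75% |
| Aimed, s = 5 mm | 16% | 39% |
| Random in a 20 mm radius disc | 2% | 6% |
| Random in a half-disc of that radius | 4% | 10% |

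So the risk depends mainly on how the location rule is read.

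**3. Effect on the contrasts.** Suppose the device does nothing. Let a_C and a_T be the scar effects at the control and lower-face sites, and b_T the effect of sampling displaced skin at the lower face. Then:

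- control change = a_C
- lower-face change = a_T + b_T
- difference in changes = a_T + b_T − a_C

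The D180-only contrast carries the same term, plus any natural difference between the two sites.

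| a_C, a_T, b_T (arbitrary units) | Control change | Lower-face change | Difference |
|---|---|---|---|
| 1, 1, 0 | 1 | 1 | 0 |
| 1, 0, 0 | 1 | 0 | −1 |
| 1, 0, 0.5 | 1 | 0.5 | −0.5 |
| 0, 0, 0.5 | 0 | 0.5 | 0.5 |
| 0, 1, 0.5 | 0 | 1.5 | 1.5 |

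A single-site change is biased when its own artefact is not zero. The between-site contrast is unbiased only when a_T + b_T = a_C. Outcome 10 is worded as a change from baseline with no between-site comparison, so cancellation between sites does not protect it as written.

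**The case against.** **The sites are zones.** The 2 cm limits describe areas, and an adjacent punch in the same area could be called the same location. An image showing the first punch can also help the operator miss it. This stands: scar sampling is a risk under the literal reading, not a certainty. A reader might infer that every control sample will be scar; the documents do not support that. They do not instruct re-siting within the zone either, so the low figures for random placement are no reassurance.

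**The reading of location must be consistent.** If it means original skin, both sites may be scarred and the artefacts could cancel between sites. If it means a landmark with an adjacent punch, the control is clean. The point about cancellation stands. At a non-surgical control, however, skin and landmark coincide, so the two readings part only at the lower face, and the protocol contains no offset.

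**Redraping is not described.** A reader might infer that the flap is lifted, redraped and trimmed, so that different skin is certainly sampled. Section 7.2 mentions only a flap and the investigator's usual technique. Displacement or excision is possible, but its extent is not given.

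**Direction.** A reader might infer that a scarred control flatters the device. That needs scar at the control alone; other combinations reverse the sign or give zero.

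**Detection.** Section 4.3.4.1 already has all slides examined by a board-certified pathologist with H&E, trichrome and an elastic-fibre stain, so scar might well be noticed. But no flag is recorded and no analysis uses one.

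**Scale.** This is a descriptive post-market study of at most 10 subjects. That limits the consequences, but biopsy change is the first listed outcome.

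**Conclusion.** The concern holds as a defect in a stated rule. Read literally, Sections 4.3.4.1 and 7.2 direct the D180 punch back to the baseline punch, and nothing tells the operator to avoid it. Depending on offset and punch size, anything from none to all of the control sample could be healed wound. At the lower face, scar and different skin are both possible. Change from baseline in outcomes 1 and 10 may therefore not be separable from these artefacts, and the between-site contrast has a bias of unknown sign unless the artefacts match.

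It would go too far to say that the change is an artefact at both sites. A device effect could still be present; it could not be isolated.

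The conclusion rests on assumed offsets, on the premise that repair tissue affects the readouts, and on the possibility that skin near the flap moves. A related inconsistency adds to it: Section 4.3.4.1 places the second sample in an untreated area of the lower face, whereas outcome 1 needs treated skin. The former may mean not yet treated, or outside the treated field.

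**What to change.** 1. In Section 4.3.4.1, replace the same-location rule with wording such as: *in the same defined zone, adjacent to and not overlapping the baseline punch, centres more than one punch diameter apart plus a stated margin, distance recorded*. If the two punches differ in size, use the larger diameter. Geometry alone requires 3 to 5 mm; the margin for healing and placement error is a judgement that the sponsor should justify.
2. State whether the lower-face location means original skin or facial landmark, and record whether the baseline punch site lay in retained or excised skin.
3. Reconcile the untreated lower-face area in Section 4.3.4.1 with the treated portion in outcome 1, so that the D180 sample represents skin documented as treated.
4. Align Section 7.2 so that the image is used to find the zone and avoid the first punch.
5. Have the existing pathologist flag scar in every D180 sample, and report outcomes 1 and 10 with and without flagged samples. Exclusion alone could leave little data from at most 10 subjects.

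The cost is a wording amendment, a short site instruction and a few recorded items, with no added biopsies. The paired samples will lie a few millimetres or more apart, which adds slight local variation.

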Brief Study Overview:	
This is a prospective single-arm, study of up to 10 study subjects undergoing a lower facelift surgery. The objective is to evaluate the effect of radiofrequency energy and/or helium gas plasma generated by Apyx Renuvion APR system on indicators of skin quality. The study will be conducted at up to three (3) investigational centers in the United States. Subjects will receive a lower facelift surgery and treatment with the Renuvion APR System.
 
Two 3-5mm punch biopsy tissue samples will be taken during the facelift procedure prior to use of the Renuvion APR System and at the Day 180 visit. Tissue samples will be assessed via microscopy, histology, and immunohistochemistry for biological markers of elasticity (collagen density, elastin, fibrillin-1) and hydration ([aquaporin-3, acidic glycosaminoglycans (GAGs), HA]). Additionally, DNA methylation will be measured in tissue samples to estimate the biological age of the skin.
 
The lower facelift surgery will be performed as per the investigator's standard clinical practice. The Renuvion APR System treatment will be performed using 4 treatment passes with settings of 80% and 1.5 LPM of helium flow with an activation speed of approximately 1-3cm/s; the mid/upper-face area will not be treated with Renuvion and the lower face/neck area will be treated with Renuvion
 
Follow-up will occur 1 day, 2 days (optional), 7 days, 14 days, 45 days, 90 days, and 180 days post-procedure with images and skin quality measurements taken as described

Protocol Number: APX-21-04

Effective Date: March 19, 2024

Revision No: 7.0

Title: Histological Evaluation of Human Skin Biopsies to Assess the Effects of Renuvion APR Treatment as an Adjunct Procedure in Facelift Surgery

	above at baseline for evaluation. Subjects may also be seen back for follow-up at the investigator's discretion.
Number of Sites Enrolling Participants:	Subjects will be recruited from up to 3 US study sites.
Sample Size:	N = up to 10 treated subjects; subjects enrolled may be greater than subjects treated.
Subject Population:	Healthy, female and male adult subjects ages 18 – 75 years old who meet the inclusion/exclusion criteria.

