### 3. STUDY PURPOSE

The purpose of this study is to gather quantifiable data on Renuvion's impact on skin elasticity and hydration, indicators of skin quality and estimate the biological skin age using DNA methylation.

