### 4. STUDY DESIGN AND ENDPOINTS

#### 4.1 DESCRIPTION OF THE STUDY DESIGN

This study is a prospective, single-arm clinical study to be conducted at up to three clinical sites in the US. Up to 10 subjects will be enrolled and treated if they meet the inclusion/exclusion criteria and provide written informed consent.

Enrolled subjects meeting all entrance criteria and confirmed eligible for study treatment will be asked to participate. Subjects will receive a lower facelift surgery per the Investigator's standard clinical practice and treatment with the Renuvion APR System. The mid/upper-face area will not be treated with Renuvion and the lower face/neck area will be treated with Renuvion. Treatment will consist of subdermal coagulation of soft tissue using the Renuvion APR handpiece.

Standardized images will be taken prior to treatment and during each follow-up visit using the site's camera system. Baseline assessments and pre-treatment images should be obtained within 30 days of the study treatment.

 Apyx Medical Corporation	
Protocol Number: APX-21-04	Effective Date: March 19, 2024 Revision No: 7.0
Title: Histological Evaluation of Human Skin Biopsies to Assess the Effects of Renuvion APR Treatment as an Adjunct Procedure in Facelift Surgery	

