## 4.3 STUDY OUTCOME MEASURES

1. Change in histology evaluation of biopsy tissue between the untreated portion of the face and the Renuvion treated portion at the D180 visit and compared to baseline.
2. Analysis of all adverse events through the D180 follow-up visit.
3. Analysis of bruising post-procedure.
4. Analysis of swelling post-procedure.
5. Healing profile.
6. Analysis of bleeding during surgery.
7. The Principal Investigator will complete a PGAIS assessing overall aesthetic improvement in the treatment area at day 45, 90, and 180 post-treatment.
8. The subject will complete a SGAIS assessing overall aesthetic improvement in the treatment area at day 45, 90, and 180 post-treatment.
9. The subject will complete a Patient Satisfaction Questionnaire (PSQ) at the 180-day follow-up visit.
10. Change in estimated biological skin age from baseline to D180.

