#### 4.3.4.8 DNA METHYLATION

Tissue samples at baseline and at D180 will be assessed for a skin-specific age predictor (DNA methylation analysis).

DNA methylation (DNAm) is a process that undergoes predictable age-dependent modifications. A highly accurate skin-specific age algorithm will analyze these modifications related to human skin health and molecular aging – quantifying the skin health/skin age of the tissue beyond the chronological age of the subject. Hallmarks of aging include genomic instability, telomere attrition, epigenetic alterations, loss of proteostasis, deregulated nutrient sensing, mitochondrial dysfunction, cellular senescence, stem cell exhaustion, and altered intercellular communication.

When available, biopsy tissue remaining after assessments via microscopy, histology, and immunohistochemistry for biological markers of elasticity (collagen density, elastin, fibrillin-1) and hydration (HA) will be transferred to the University of Miami and then processed using the Illumina Human Methylation EPICv2 array for DNAm data. These data will be analyzed to determine if Renuvion treatment is able to reverse or improve DNAm age.

Apyx Medical Corporation

Protocol Number: APX-21-04

Effective Date: March 19, 2024

Revision No: 7.0

Title: Histological Evaluation of Human Skin Biopsies to Assess the Effects of Renuvion APR Treatment as an Adjunct Procedure in Facelift Surgery

Any remaining tissue sample following the DNAm analysis will be destroyed.

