## 10. STATISTICAL METHODOLOGY

### 10.1 STATISTICAL AND ANALYTICAL PLANS

For the purposes of this post-market study, descriptive statistics will be performed.

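### Facelift and Renuvion are always given together on the same flap, so the data can show only their combined effect; the attribution to Renuvion alone needs rewording and the within-subject contrast needs defining

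*Combined protocol and SAP*

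**What the plan says.** The synopsis describes the design: "This is a prospective single-arm, study of up to 10 study subjects undergoing a lower facelift surgery". Section 4.1 gives everyone both components: "Subjects will receive a lower facelift surgery per the Investigator's standard clinical practice and treatment with the Renuvion APR System". Section 7.2 puts the device on the dissected tissue: "the Renuvion APR System will be used in open surgery between the skin and SMAS on the neck, submentum, and lower facial skin flap".

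Section 4.3.4.1 takes two biopsies per subject, one near the root of the helix and hairline and one from the cheek in the lower face. Both are taken before any Renuvion treatment and repeated at the same places at Day 180. It then states: "The untreated skin tissue samples from non-surgical sites for each subject will be provided as control specimen".

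In section 4.3, outcome 1 compares untreated with Renuvion-treated skin at Day 180 and also refers back to baseline, without a formula. Outcome 10 is "Change in estimated biological skin age from baseline to D180", with no site named.

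The aims are worded as device effects. Section 3 seeks data on Renuvion's "impact on skin elasticity and hydration, indicators of skin quality and estimate the biological skin age using DNA methylation". Section 4.3.4.8 says: "These data will be analyzed to determine if Renuvion treatment is able to reverse or improve DNAm age". The study purpose and overview in the synopsis, and the background in section 2.1, use similar wording. Section 10.1 gives the whole analysis plan: "For the purposes of this post-market study, descriptive statistics will be performed".

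**The concern.** Lower-face skin at Day 180 has been undermined, put under tension, healed and exposed to Renuvion. The control skin has had none of these. A difference between them, however clean, belongs to the operation as a whole. If the report follows the wording of sections 3 and 4.3.4.8, it will credit the device with an effect that the facelift may have produced in part or in full.

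A second, smaller problem is that the plan does not say which contrast it will use. A comparison of the two sites at Day 180 alone keeps any difference between them that existed before surgery. A before-after change at the lower face alone keeps whatever changed with time at both sites. The samples allow both to be removed, but the plan does not commit to doing so.

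**Working it through.** The plan gives no alpha, power, effect size or SD, and no derivation for its figure of up to 10 treated subjects, so there is no calculation of its own to reproduce. The question is what the planned samples can identify.

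**Step 1: what each sample contains.** Let m be the control-site baseline mean, S a constant site difference, T change over time common to both sites, F the facelift effect and R the Renuvion effect. The lower-face biopsy is taken to be treated skin at Day 180, as outcome 1 requires.

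| Site | Baseline | Day 180 |
|---|---|---|
| Control (upper) | m | m + T |
| Lower face | m + S | m + S + T + F + R |

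There are five unknowns and four cell means, and the design matrix has rank 4 of 5. S, T and the sum F + R are estimable. F alone and R alone are not, because they occur only together in one cell.

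**Step 2: what each possible contrast estimates.**

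- Day 180 only, lower face minus control: S + F + R.
- Lower face, Day 180 minus baseline: T + F + R.
- Difference of changes, (lower-face Day 180 minus baseline) minus (control Day 180 minus baseline): F + R.

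The third removes S and T but still leaves F + R. Adding facelift-only subjects with the same two sites and times would raise the rank to 5 of 5 and separate R. If change over time differs between the sites (T_lower not equal to T_upper), the third contrast becomes F + R + (T_lower − T_upper), so it rests on parallel change.

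**Step 3: elapsed time in a lower-face before-after reading of outcome 10.** The Day 180 window in the schedule table is 165 to 195 days.

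- 165/365.25 = 0.45 years
- 180/365.25 = 0.49 years
- 195/365.25 = 0.53 years

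Ageing would raise estimated age, so it works against a finding of reversal.

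**Step 4: precision of the recommended contrast.** The documents give no SD or correlation. Assume a common SD of 1 and equal correlation rho among a subject's four samples. The weights are +1, −1, −1, +1, so the variance is 4(1 − rho). At n = 10, with t on 9 degrees of freedom = 2.262, the 95% half-width is 2.262 × sqrt(4(1 − rho)/10):

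- rho = 0.3: 2.262 × sqrt(0.28) = 1.20 SD
- rho = 0.5: 2.262 × sqrt(0.20) = 1.01 SD
- rho = 0.7: 2.262 × sqrt(0.12) = 0.78 SD

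A two-sample paired difference at rho = 0.5 gives 2.262 × sqrt(2 × 0.5/10) = 0.72 SD. Under these assumptions the four-sample contrast is therefore wider by sqrt(2).

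Fewer complete sets widen it further. In units of the contrast's own SD the half-width is 0.72 at n = 10, 0.84 at n = 8 and 1.05 at n = 6 (8 and 6 are assumed). At rho = 0.5 the contrast's SD is sqrt(2) = 1.414, which gives 0.836 × 1.414 = 1.18 SD at n = 8 and 1.049 × 1.414 = 1.48 SD at n = 6.

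**The case against.** The strongest reply is that this is a small, post-market, descriptive study with no hypothesis and no success criterion. Its title calls Renuvion an adjunct to facelift surgery, and section 2.2.2 speaks only of improvement following use of the system. This limits how serious the point is. It does not remove it, because asking whether Renuvion reverses methylation age is a causal question however the numbers are summarised.

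Several stronger readings are tempting, and the documents do not support them:

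- *Site and ageing effects cannot be separated.* They can: both sites are sampled at both times, and outcome 1 already points towards a comparison against baseline. What is missing is the formula.
- *Descriptive analysis causes the problem.* It does not. A hypothesis test on the same samples would leave facelift and Renuvion equally confounded, and section 10.1 does not rule out paired differences or intervals.
- *Outcome 10 excludes the control samples.* It names no site, and section 4.3.4.8 excludes neither.
- *Pairing will sharpen the result.* At a correlation of 0.5, a two-sample paired difference (0.72 SD) is narrower than a comparison of two unpaired means, 2.101 × sqrt(2/10) = 0.94 SD. That is not the contrast needed here, which is 1.01 SD.
- *GAIS and PSQ are credited to Renuvion.* The protocol asks for overall improvement in, and satisfaction with, the treatment area or treatment. It needs only a statement that these rate the whole operation.

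Two practical objections stand. Fibre integrity is scored semi-quantitatively, so double differences and t-type intervals need care. Methylation uses leftover tissue only when available, so some subjects may lack all four samples.

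**Conclusion.** The point holds in this form: the design can estimate the combined effect of facelift plus Renuvion and nothing narrower, so the attribution to Renuvion alone is unsupported whatever the results. This follows from the design and needs no numerical assumption. The facelift's share of any difference cannot be estimated from these data.

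The undefined contrasts are a separate and curable gap. The difference of changes removes constant site differences and common ageing, provided change over time is parallel at the two sites. Its merit is less bias, not more precision. The half-widths of 0.78 to 1.20 SD at n = 10 are illustrations under assumed equal correlations. The 0.45 to 0.53 years is elapsed time, and the documents give no precision for the methylation clock against which to judge it.

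One inconsistency bears on all of this. Section 4.3.4.1 locates the second biopsy in a part of the lower face described as untreated, near the treatment line and resampled at the same place, whereas outcome 1 needs Renuvion-treated skin at Day 180. Figure 3 was not available to check. Until these passages are reconciled, it is unclear that the lower-face sample represents treated skin.

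This should be fixed. It is a matter of claims and specification in a descriptive study, not a reason to stop it.

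**What to change.** 1. In section 3, section 4.3.4.8, the synopsis purpose and overview, and the closing part of section 2.1, replace the device-alone wording with *change after lower facelift with adjunct Renuvion*. State that GAIS and PSQ rate the whole operation. Keeping a device-alone claim would require a facelift-only comparator.
2. In section 10.1, define the contrast for outcomes 1 and 10 in each subject as (lower-face Day 180 minus baseline) minus (control Day 180 minus baseline). Report individual plots and a mean or median with 95% CI, using a rank-based summary for semi-quantitative scores. Report the number of subjects with all four samples, and state the parallel-change assumption.
3. Reconcile the description of the second biopsy site in section 4.3.4.1 with the treated skin that outcome 1 requires.

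The cost is a paragraph in section 10 and rewording elsewhere, with no new subjects, visits or biopsies. The downsides are a less favourable claim, a possibly wider interval, and fewer usable subjects for methylation where leftover tissue is missing.

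### With the biopsies placed as the plan implies, no planned contrast separates Renuvion from the facelift, yet the stated purpose is Renuvion's own effect

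*Combined protocol and SAP*

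**What the plan says.** **Purpose.** Section 3 states: "The purpose of this study is to gather quantifiable data on Renuvion's impact on skin elasticity and hydration". The Synopsis gives the same purpose, and its overview sets the objective as the effect of the energy delivered by the system. Section 2.1 says that the device's effect on the skin markers has not yet been documented and that documenting it is the aim. Section 4.3.4.8 says of the methylation data: "These data will be analyzed to determine if Renuvion treatment is able to reverse or improve DNAm age".

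**Design.** Section 4.1: "This study is a prospective, single-arm clinical study to be conducted at up to three clinical sites in the US". Synopsis: "Subjects will receive a lower facelift surgery and treatment with the Renuvion APR System". Section 7.2: "For all subjects the Renuvion APR System will be used in open surgery between the skin and SMAS on the neck, submentum"; the sentence goes on to include the lower facial flap. The mid and upper face get no Renuvion. The facelift itself follows each investigator's usual practice.

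**Samples.** Section 4.3.4.1 takes two punches from the left face, during surgery but before the device, and again at Day 180 in the same places. One is near the root of the helix and the hairline. Of the other it says: "The second tissue sample will be obtained from cheek skin in the untreated area of the lower face within 2 cm of the treatment line". Of the comparator it says: "The untreated skin tissue samples from non-surgical sites for each subject will be provided as control specimen".

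**Contrasts and analysis.** Outcome 1 (Section 4.3) compares untreated with Renuvion-treated skin at Day 180, and with baseline. Outcome 10 is the change in estimated skin age from baseline to Day 180. Section 10.1 plans descriptive statistics only.

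**The concern.** The purpose asks what Renuvion does. Skin in the device field has been surgically raised as well as exposed to plasma, and by Day 180 it has been through the healing that follows both. The control is described as non-surgical, so it has had neither. Subtracting it removes what the subject's two sites share, including the passage of time, but not the surgery.

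What is at stake is attribution. A change in collagen, elastin, fibrillin-1, hyaluronic acid or methylation age could come from the operation, the device or both, and the current wording allows all of it to be credited to the device.

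**Working it through.** The plan derives no sample size, power or effect size, so there is no figure to reproduce. The question is whether the device effect can be estimated at all.

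**Inputs.** Two sites and two times (Section 4.3.4.1); facelift and device in every subject (Synopsis, Sections 4.1 and 7.2). I take the lower punch as device-treated (Outcome 1) and the upper punch as non-surgical (Section 4.3.4.1). The baseline punch is taken during the operation; I assume it carries no healing effect yet.

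**Model.** Mean = μ + s (lower site) + t (Day 180) + F (facelift) + R (device).

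| Cell | Mean |
|---|---|
| Upper, baseline | μ |
| Upper, Day 180 | μ + t |
| Lower, baseline | μ + s |
| Lower, Day 180 | μ + s + t + F + R |

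**Contrasts.**
- Lower-site change from baseline: (μ + s + t + F + R) − (μ + s) = t + F + R.
- Lower minus upper at Day 180: (μ + s + t + F + R) − (μ + t) = s + F + R, so anatomical site is mixed in too.
- Difference of the two changes: (t + F + R) − t = F + R, provided the two sites would otherwise have changed alike.

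F and R are both 1 in one cell and both 0 in the other three, so their columns are identical. The design matrix has rank 4 for 5 parameters. F + R is estimable; F alone and R alone are not. More subjects would not change this.

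**Size.** The device share is R/(F + R). The documents give no F, so these ratios are assumptions, with F and R in the same direction:

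| Assumed F | Device share |
|---|---|
| 0 | 100% |
| R/2 | 1/1.5 = 67% |
| R | 1/2 = 50% |
| 2R | 1/3 = 33% |
| any F > 0, with R = 0 | 0% |

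**Sensitivity to punch location.**
- *Upper site inside the facelift field.* Its Day 180 mean becomes μ + t + F, and the difference of changes is (t + F + R) − (t + F) = R. The device effect is then estimable, if the facelift acts equally at both sites and their other trends are parallel.
- *Lower punch not exposed to the device,* as Section 4.3.4.1 read literally suggests, with the upper site non-surgical. The difference of changes is F if that skin was lifted and 0 if it was not. It contains no R.
- *A facelifted, device-free lower-face sample at Day 180* would raise the rank to 5 of 5. The plan names no such comparator.

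**Other outcomes.** PGAIS and SGAIS (Section 4.3.4.2) and the PSQ (Appendix A) are rated against pre-treatment photographs, so they reflect the whole procedure. Bruising, swelling, healing and bleeding have no facelift-only reference.

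**The case against.** The best defence is that this is a small, descriptive, post-market study with no hypothesis test, and that its title presents Renuvion as an adjunct. That limits the damage but does not remove it. A descriptive mean of F + R is still not a description of R, and Sections 3 and 4.3.4.8 still promise R.

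Three stronger readings are tempting, and the documents do not support them.

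- *The study can never show a device effect.* This depends on where the punches lie. Only one phrase puts the control outside the surgical field; elsewhere the mid and upper face is described only as not receiving Renuvion, and surgical extent is left to the surgeon. The lower punch is itself described as untreated. Under either alternative the contrasts mean something different, as shown above.
- *Every outcome promises a device-only effect.* Section 2.2.2 speaks of improvement after use of the system, which is a statement of timing. Outcomes 3 to 9 make no device-only claim. The control site's own change contains neither effect.
- *A device with no effect would almost always look beneficial.* Under normality, the chance that a mean of 10 differences exceeds zero when R = 0 is Φ(F√10), with F in SD of the within-subject difference: 79% at F = 0.25 and 94% at F = 0.5. But it is already 50% at F = 0. The plan gives neither the sign nor the size of F, and no rule that a mean above zero counts as improvement. How the results will be reported is also unknown.

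**Conclusion.** The concern holds conditionally. If the lower punch is device-treated and the control is non-surgical, every planned contrast between treated and control skin, or between treated skin and its baseline, estimates at best facelift plus device. None answers the question as worded in the Synopsis and Sections 2.1, 3 and 4.3.4.8. With both effects in the same direction, the device share can lie anywhere from 0 to 100%, and nothing in the data would narrow it.

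The two conditions come from the plan's own text, but that text conflicts with itself on the lower punch and is thin on the control. Stating the locations is therefore part of the correction. The study can still describe change after the combined procedure. I would class this as should-fix.

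**What to change.** 1. **Wording.** In the Synopsis (purpose and overview) and Sections 2.1, 3 and 4.3.4.8, describe the target as the change after lower facelift with adjunct Renuvion. State in Sections 4.3 and 10.1 that Outcomes 1 and 3 to 10 will not be attributed to Renuvion alone.
2. **Locations.** Reconcile Section 4.3.4.1 (second punch in untreated skin, same places at Day 180, control from non-surgical sites) with Outcome 1, which needs a Renuvion-treated portion. State where each punch lies relative to the facelift field and to the Renuvion field.
3. **Recording.** For each punch, record on the CRF whether the skin was undermined, whether it was exposed to Renuvion, and the distances to the incision and to the treatment line. Report the contrasts alongside this information.

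I would not move the control punch to undermined, device-free skin in order to report a device contrast in a subset. The subset would be selected by surgeon from at most 10 subjects at up to three sites, and anatomical site would remain confounded.

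The cost is an amendment, a few CRF fields and a narrower claim. No extra biopsy or subject is needed.
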